3.5. Dose Escalation/De-escalation

For Parts A, B, and C of the study (healthy subjects), safety and drug exposure will determine escalation or de-escalation. If the initial dose tested in Part A had not been well tolerated, the Sponsor may have chosen to de-escalate until a well-tolerated dose was identified. A careful analysis of available safety, laboratory evaluation, and drug PK data in healthy subjects was done to determine the starting dose for Part D in subjects with CG. A careful analysis of available safety, laboratory evaluation, and drug PK data in subjects with CG will determine the starting dose for Part E in subjects with GALK-deficient Galactosemia. The starting dose in Part E will not be higher than the highest acceptable dose used in Part D at the time of starting Part E. The starting dose in Part D Extension will be 20 mg/kg based on acceptable SAD and MAD safety and PK data from Cohort D2.

For Part D of the study (subjects with CG), safety, drug exposure, and biomarker analysis of galactitol will determine escalation or de-escalation. If the drug exposure in subjects with CG is similar to that seen in healthy subjects in Part A, the same or similar approach to dose escalation may be utilized. If there is any concern of altered drug exposure or drug clearance based on PK analysis after the single dose in the initial cohort of Part D, then alternative dose escalation to lower levels may be selected until the relationship between dose and exposure in subjects with CG is determined. Dose escalation may be stopped if an effect on galactitol (reduction in galactitol) is achieved, but it becomes apparent that higher drug exposure is not increasing reduction of galactitol or providing any additional benefit. If any tested dose is not well tolerated

while markedly reducing galactitol levels, lower dose levels may be tested until no/minimal reduction in galactitol levels is detected.

In case of multiple cohorts in Parts E, the dose escalation process will be the same as for Part D.

A second cohort of the Part D Extension (DE2) may be initiated to evaluate a dose higher than 20 mg/kg/day if this dose was well tolerated in the SAD and MAD portions of the study in both healthy volunteers and subjects with CG.

The SRC will make recommendations to the Sponsor regarding dose escalation or de-escalation for each cohort based on the results from the previous cohort as described in [Section 3.4](#). The Sponsor will act upon this recommendation and inform the Investigator(s) and the IRB(s)/IEC(s).

The SRC will pay particular attention to DLTs defined as any AT-007-related AE or clinically relevant finding on laboratory tests, ECGs, vital signs, or physical examinations that, in the opinion of the Investigator and/or the SRC, precludes administering the dose to any subject and/or continuing to administer daily doses to the subject who experienced the event. Specific individual subject-level dose stopping criteria for hepatic and renal toxicity are described in [Appendix G](#) and [Appendix H](#). For DLTs, as well as fatal serious adverse events (SAEs) and life-threatening SAEs, breaking the blind will be considered and initiated (as needed) per SRC discussion and agreement.

Dose-escalation will be stopped and de-escalation initiated if:

- ≥ 2 subjects on AT-007 (B and C cohorts of the same dose level considered together) experience a DLT at any time through 24 hours after the last dose of study treatment
- Any subject on AT-007 has a fatal SAE or life-threatening SAE requiring urgent intervention at any time through 24 hours of the last dose of study treatment

The maximum tolerated dose (MTD) will be the dose level below the dose level at which one or more of the events listed above occurs.

Dose escalation within each part of the study will continue until the MTD is identified per the rules described earlier in this section or the SRC and/or Sponsor decide to stop dose escalation. Dose de-escalation, if initiated within any part of the study, will continue until the MTD is identified or the SRC and/or Sponsor decide to stop.

If the events outlined in the above MTD definition do not occur at any dose level in a study part, then the MTD will be the highest dose level in that study part.

If the events outlined in the above MTD definition occur at any given dose level, the Sponsor may decide to investigate a dose higher than the previously well-tolerated dose but lower than the dose at which one of the events outlined in the above MTD definition occurred.

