3.3.2. Part B: Double-blind Multiple Ascending Dose (MAD) in Healthy Subjects

Four dose levels are planned for the MAD group in Part B ([Table 3](#)). Subjects will be enrolled in 4 sequential cohorts of 6 or 8 subjects each, for a total of 28 subjects. The initial dose level for Part B (5 mg/kg) was based on the results from Part A Cohorts A1 through A4. Subjects will receive study drug (AT-007 or placebo) QD for 7 consecutive days. Subjects will be housed at the CRU for observation from Day -1 (day before the first dose) through at least 48 hours after the last dose. Subjects will return for the EOS Visit at 28 days after the last dose. Progression to and the dose level for the next cohort will be dependent upon safety data through Day 8 from the previous cohort as well as results from Part A. The Schedule of Assessments for Part B is provided in [Appendix B](#). Maximum duration of study participation (Screening through EOS Visit) for an individual subject will be approximately 63 days.

Table 3: MAD Dose Cohorts in Healthy Subjects (Part B)

Cohort	Dose	
B1	AT-007 oral capsule QD for 7 consecutive days, dose 5 mg/kg (n=6)	placebo (n=2)
B2	AT-007 oral capsule QD for 7 consecutive days, dose 10 mg/kg (n=4)	placebo (n=2)
B3	AT-007 oral capsule QD for 7 consecutive days, dose 20 mg/kg (n=6)	placebo (n=2)
B4	AT-007 oral capsule QD for 7 consecutive days, dose 40 mg/kg (n=4)	placebo (n=2)

n = number of subjects; MAD = multiple ascending dose; QD = once daily.

Note: The number of cohorts and total number of subjects may increase if doses above 40 mg/kg are tested in additional cohorts (see [Section 1.4](#)). The numbers of subjects in the cohorts are intended to ensure at least 6 subjects on AT-007 at each well-tolerated dose level when Cohort C subjects at the same dose level are considered. This table has been updated to reflect the dose levels actually tested in completed Cohorts B1, B2, and B3 and the planned dose in Cohort B4.

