3.4. Safety Review Committee (SRC)

An SRC consisting of the Principal Investigator(s) or designee (e.g., a medically qualified sub-investigator), the pharmacokineticist, and Sponsor (including external consultants) will meet and review the safety data from each cohort in each part of the study. Study progression to the next cohort (within each part of the study) will occur only after review of the safety data through Day 3 in Part A, Day 8 in Parts B and C, and Day 12 in Parts D and E.

Safety data to be assessed prior to each dose escalation decision within a part of the study include but are not limited to the following:

- AEs (including dose-limiting toxicities [DLTs], see [Section 3.5](#))
- Clinical safety laboratory tests (hematology, chemistry, coagulation, urinalysis)
- Physical examinations
- Vital signs
- ECGs

In addition, PK data for AT-007 will be considered during all parts of the study. PK data will be evaluated by the Sponsor rather than the SRC. Safety and PK data from Cohorts A1 through A4 in Part A were evaluated by the SRC (safety) and Sponsor (PK) before Part B (MAD) was allowed to start. Safety and PK data from Cohorts A1 through A4 in Part A and Cohorts B1 and B2 were evaluated before Cohort C1 (MAD with lumbar puncture) or Cohort D1 (subjects with CG) were allowed to start. Safety and PK data from these cohorts plus Cohort D2 (and possibly Cohorts A5, B4, and D3, depending on timing) will be evaluated before Cohort E1 (subjects with GALK-deficient Galactosemia) will be allowed to start. (Notes: Cohort A5 [40 mg/kg] was added as part of the amendment resulting in protocol version 4.0 and completed before the writing of protocol version 5.0. Addition of Cohort A5 resulted in the addition of Cohort C3 [as part of the same protocol amendment that added Cohort A5] and will result in Cohorts B4 and D3 [both not yet used as of the writing of protocol version 5.0] being conducted.) Safety and PK data from Cohort D2 were evaluated before deciding the dose (20 mg/kg) for Cohort DE1.

The review of the PK data from Cohorts A1 through A4 and the first 2 cohorts of Part B confirmed that once daily (QD) dosing is adequate.

Safety and PK data from Cohorts A1 through A4 and Cohorts B1, B2, and B3 were evaluated before Cohort C2 (MAD with lumbar puncture) was allowed to start.

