6.5.4. Day 6 (Study Drug Dosing Day)

The following procedures will be done on Day 6:

- Perform physical examination including weight
- Measure vital signs
- Collect fasting blood sample(s) for clinical laboratory testing (hematology, coagulation and biochemistry)
- Collect fasting urine sample for urinalysis and, for female subjects of childbearing potential only, urine pregnancy test (pregnancy test must be negative for the subject to receive study drug)
- Administer study drug at approximately the same time of day as on Day 1
- Feed the subject (3 meals with breakfast provided at ≥ 2 hours postdose)
- Fast the subject overnight for at least 10 hours
- Collect AE and concomitant medication data throughout the day

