- i: On Day 1, blood samples for PK will be collected predose (within 60 minutes before the dose) and at 0.5, 1, 1.5, 2, 4, 6, 8, and 12 hours (± 5 minutes for all time points) after the dose. On Day 2, blood samples for PK will be collected predose (i.e., at 24 hours ± 5 minutes after the Day 1 dose and before the Day 2 dose). On Day 7, blood samples for PK will be collected predose (within 60 minutes before the dose) and at 0.5, 1, 1.5, 2, 4, 6, 8, and 12 hours (± 5 minutes for all time points) after the dose. Also, blood samples for PK will be collected at 24, 36, and 48 hours (± 5 minutes for all time points) after the Day 7 dose; these collections will be taken on Day 8 and Day 9.

**APPENDIX C. SCHEDULE OF ASSESSMENTS FOR PART C (MAD IN
HEALTHY SUBJECTS)**

Schedule of Assessments for MAD in Healthy Subjects (Part C)

PROCEDURE	Screening (Days -28 to -1)	Day -1 ^a (Check-in)	Day 1	Day 2	Days 3, 4, & 5	Day 6	Day 7	Day 8	Day 9 ^a (Check-out)	EOS Visit ^b (Day 35±2)
Check-in		X ^a								
Discharge									X ^a	
Informed consent	X									
I/E criteria	X	X								
Medical history/updates	X	X								X
Demographic data	X									
Physical examination ^c	X	X				X			X	X
Vital signs ^d	X	X	X	X		X	X	X	X	X
Electrocardiogram ^e	X	X	X				X			X
Clinical laboratory testing (biochemistry, hematology, coagulation, urinalysis) ^f	X	X				X				X
HIV and hepatitis B & C testing	X									
Urine drug/cotinine screen	X	X								
Pregnancy test (female subjects) ^g	X	X				X				X
Drug administration ^h			X	X	X	X	X			
Blood sample collection for PK analysis ⁱ			X	X			X	X	X	
Lumbar puncture ^j							X			
Adverse events									Throughout Study	
Prior/Concomitant medications	X								Throughout Study	

CSF = cerebrospinal fluid; EOS = end-of-study; FSH = follicle-stimulating hormone; HIV = human immunodeficiency virus; I/E = inclusion/exclusion; MAD = multiple ascending dose; PK = pharmacokinetic; QD = once daily.

a: Check-in will occur around 11 am on Day -1 and Discharge will occur on Day 9 after the blood sample for PK is collected at 48 hours after the Day 7 dose and all Day 9 procedures are done.

b: The EOS visit will be scheduled for 28 (±2) days after the last dose of study drug.

- c: All physical examinations will include weight; however, height will be measured only at screening.

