3.2.2 Clinical Laboratory Assessments

A Clinical Laboratory Improvement Amendments certified laboratory will perform the following clinical laboratory tests:

- Hematology: hemoglobin, hematocrit, total and differential leukocyte count, RBC, and platelet count
- Serum chemistry: albumin, blood urea nitrogen (BUN), creatinine, total bilirubin, alkaline phosphatase (ALP), aspartate transaminase (AST), alanine transaminase (ALT), sodium (Na+), potassium (K+), chloride (Cl-), lactate dehydrogenase (LDH), calcium (Ca), uric acid, glucose, direct bilirubin (DB), and gamma-glutamyl transferase (GGT)
- Coagulation: prothrombin time (PT) and international normalized ratio (INR)
- Serology: blood tests for hepatitis B surface antigen, hepatitis C antibody, and HIV.
- Urinalysis by an automated or manual urine "dipstick" method: pH, specific gravity, protein, glucose, ketones, bilirubin, blood, nitrite, leukocyte esterase, and urobilinogen. If protein, occult blood, nitrite, or leukocyte esterase values are out of range, a microscopic examination will be performed.
- Urine drug screen: drugs of abuse (amphetamines, benzodiazepines, barbiturates, cannabinoids, cocaine, opiates)
- Urine cotinine screen (subjects in Parts A, B, and C only)
- Pregnancy test (all female subjects of childbearing potential)
- FSH (for female subjects claiming postmenopausal status)

For Parts D, E and D Extension only, the following tests will be done in addition to the ones listed above:

- GALT (Part D and Part D Extension but only done once for subjects participating in both Parts) or GALK (Part E) activity in red blood cells
- GALT (Part D and Part D Extension but only done once for subjects participating in both Parts) or GALK (Part E) gene analysis
- Aldose Reductase activity (only done once for subjects participating in both Parts D and D Extension)

Fasted samples for hematology, coagulation, chemistry, and urinalysis assessments will be collected at the following time points:

- Part A: Screening, Day -1, Day 3, EOS
- Part B: Screening, Day -1, Day 6, EOS
- Part C: Screening, Day -1, Day 6, EOS
- Part D: Screening, Days -1, 6, 12, 20, 32, EOS

- Part E: Screening, Days -1, 6, 12, 20, 32, EOS
- Part D Extension: Screening, Days -1, 30, 60, 90, EOE

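### In Parts B and C the DLT rule and the safety review count laboratory findings to Day 8, but no planned safety laboratory sample falls between Day 6 and the end-of-study visit on Day 35 (±2)

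*Protocol*

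**What the plan says.** **What counts and until when.** Protocol Section 3.5 defines a DLT as "any AT-007-related AE or clinically relevant finding on laboratory tests, ECGs, vital signs, or physical examinations" that in the opinion of the investigator or the SRC precludes further dosing. Escalation stops when two or more subjects on AT-007 "experience a DLT at any time through 24 hours after the last dose of study treatment", with B and C cohorts at the same dose taken together. If no stopping event occurs in a study part, the highest dose in that part becomes its maximum tolerated dose (MTD).

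**What the SRC sees.** Section 3.4 bases progression on "safety data through Day 3 in Part A, Day 8 in Parts B and C", and its list of data to assess includes "Clinical safety laboratory tests (hematology, chemistry, coagulation, urinalysis". Section 3.3.2 repeats the cut-off: "Progression to and the dose level for the next cohort will be dependent upon safety data through Day 8 from the previous cohort".

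**When laboratory samples are taken.** Section 6.5.4 (Day 6) contains the only on-treatment draw in Part B: "Collect fasting blood sample(s) for clinical laboratory testing (hematology, coagulation and biochemistry". It is listed before that day's dose. Sections 6.5.5 and 6.5.6 list no safety laboratory sample on Days 7, 8 or 9. Section 6.6 gives Part C the same schedule apart from randomization and the lumbar puncture. Appendices B and C agree, and SAP Section 3.2.2 states "Part B: Screening, Day -1, Day 6, EOS", with an identical line for Part C.

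**What depends on it.** The SRC meeting on B4 and C3 recommends the dose for Cohort D3 (Section 3.4). D3 may start once B4 has finished everything except its end-of-study visit (synopsis). B4 safety data are also considered before a DE2 dose is chosen (Section 3.4).

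**The concern.** The stopping rule covers a period in which one of its own components has no planned observation. If nothing is reported after Day 6, the rule treats the last doses as free of laboratory DLTs, and the MTD definition turns that absence into tolerability. The hepatic and renal stopping criteria that Section 3.5 refers to (Appendices G and H) rest mainly on laboratory results, and a change in transaminases or creatinine may cause no symptoms.

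The live decision is the B4/C3 review. These cohorts are the only planned repeat-dose data at 40 mg/kg in healthy subjects. Their review leads to a dose that patients in D3 would take for 27 days, and the B4 end-of-study laboratory results need not be available when D3 starts.

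**Working it through.** **Step 1. Reproduce the plan's visit days.** The last dose in Parts B and C is on Day 7.
- End-of-study visit: 7 + 28 = Day 35, as in Section 6.5.6. The ±2-day window gives Day 33 to Day 37.
- End of the DLT window: Day 7 + 24 hours = Day 8, the same day as the SRC cut-off.

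**Step 2. Gap between planned laboratory samples.** 35 − 6 = 29 days (33 − 6 = 27 to 37 − 6 = 31).

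**Step 3. Part of the DLT window without planned laboratory follow-up.** Take the window from the first dose to 24 hours after the seventh: 7 × 24 = 168 hours.
- Draw before dose 6: 5 doses, or 5 × 24 = 120 hours, lie before it. Uncovered: 168 − 120 = 48 hours (48/168 = 29%, or 2 of 7 doses).
- Section 6 lets the draw follow the dose, provided the fast is not yet broken. The fast may end from 2 hours after the dose. With a draw at 2 hours, 168 − 122 = 46 hours remain uncovered (27%): dose 7 and nearly all of dose 6.

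**Step 4. Compare with the other parts.**

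| Part | SRC cut-off | Laboratory draw on that day? |
|---|---|---|
| A | Day 3 | Yes (Section 6.4.2, Appendix A) |
| B, C | Day 8 | No; last draw is Day 6 |
| D, E | Day 12 | Yes (Section 6.7.4, Appendices D and E) |

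Only Parts B and C depart from the pattern.

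**Step 5. What the gap could do to the stopping rule (illustration).** The documents give no DLT rate. Assume that every DLT is an asymptomatic laboratory finding, that onset is spread evenly over the seven doses, and that no unscheduled test is done. At 40 mg/kg, n = 4 (B4) + 4 (C3) = 8. With observable rate q, the chance of two or more DLTs is 1 − (1 − q)^8 − 8q(1 − q)^7.

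| True DLT rate p | All doses covered (q = p) | q = 6p/7 | q = 5p/7 |
|---|---|---|---|
| 10% | 0.19 | 0.15 | 0.11 |
| 20% | 0.50 | 0.41 | 0.32 |
| 30% | 0.75 | 0.65 | 0.54 |
| 40% | 0.89 | 0.82 | 0.72 |

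Example at p = 30%, q = 0.30 × 5/7 = 0.214: 1 − 0.145 − 0.317 = 0.54. The 6/7 column credits all of dose 6, although at most about its first 2 hours are covered if the fast ends at the earliest permitted time.

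**The case against.** **Other routes to detection exist.** Subjects stay in the unit until Day 9. Adverse events are collected daily, vital signs are taken on Days 7 to 9, ECGs on Day 7, and a physical examination on Day 9. Section 6.10 allows further tests at the investigator's discretion. A reader might infer that late laboratory DLTs cannot be seen at all. The documents do not support that: what is missing is a planned sample. An asymptomatic change gives no reason to order an unplanned one, so the narrower point stands.

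**Appendix H appears to fill the gap for renal findings.** It says eGFR and the two urine ratios (UPCR, UACR) are assessed at every visit. Appendices B and C schedule nothing of the kind on Days 7 to 9, and their laboratory row omits both ratios. This is a second inconsistency, and it would not cover hepatic or hematology findings in any case.

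**Day 6 may already reflect near-full exposure.** It is tempting to say that the uncovered doses are those with the greatest accumulation. The documents give no human half-life or accumulation ratio. Under linear kinetics the fraction of steady state after 5 daily doses is 1 − 2^(−120/h) for a half-life of h hours: 99.9% at an assumed 12 hours, 96.9% at 24 and 82% at 48 (91% after 7 doses at 48). The remaining concern is the length of dosing observed, five doses or little more against seven.

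**The cut-off need not match the DLT window.** Section 3.3 speaks of available safety data, no passage promises a Day 8 laboratory result, and in Part D the Day 12 review falls well before dosing ends on Day 32. Section 3.6 also allows the study to be discontinued for laboratory abnormalities. All of this is correct. In Parts B and C, however, the window and the cut-off do coincide, and laboratory findings belong to both.

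**Later safeguards.** D3 has its own laboratory tests on Days 6, 12, 20 and 32, and the sponsor must agree before each subject starts multiple dosing. These limit the harm, but they act only after patients have received the dose.

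**Conclusion.** The mismatch is real and rests on the text alone. In Parts B and C, 46 to 48 of the 168 hours in the DLT window have no planned laboratory follow-up before the SRC decides, and the next planned sample comes 27 to 31 days after Day 6. It concerns asymptomatic laboratory DLTs only; the other elements of the DLT definition are still observed after Day 6.

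The prospective effect is limited to B4 and C3 (8 active subjects), which both documents still write as future. Their review feeds the D3 dose, and B4 data are also considered for DE2. For the completed cohorts (B1 to B3, C1 and C2) this is a matter of accurate reporting. A reader might infer that those escalations missed a laboratory toxicity; nothing in the documents shows that.

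The probabilities in the working depend on assumed DLT rates and on every DLT being laboratory-only with even onset. They illustrate a possible loss under extreme assumptions and do not estimate it. The finding itself needs none of them.

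**What to change.** Reconcile the Part B and C laboratory schedule (protocol Sections 6.5 and 6.6, Appendices B and C, SAP Section 3.2.2) with the DLT window and Day 8 review in Sections 3.4 and 3.5, so that the laboratory data the SRC relies on cover the window that the stopping rule states. In the same edit, reconcile the every-visit renal assessment in Appendix H with Appendices B and C.

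The practical room exists. Subjects remain in the unit until Day 9, and Appendix B, footnote i, already provides a Day 8 venipuncture: "Also, blood samples for PK will be collected at 24, 36, and 48 hours" after the Day 7 dose. A laboratory tube at that draw would add a small blood volume and a laboratory charge for each subject, and the review would wait for the result from the unit's own laboratory (Section 10.5).

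For cohorts already completed, state in the study report that planned laboratory coverage ended at the Day 6 sample, so that any MTD statement is read accordingly. No dose, laboratory threshold or stopping rule is proposed here.

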6.4.1. Day 1 (Study Drug Dosing Day)

Subjects will remain in the CRU on Day 1.

The following procedures will be done before study drug administration on Day 1:

- Measure predose vital signs
- Conduct predose 12-lead ECG
- Collect predose blood sample for PK
- For Cohorts A4 and A5 only, collect predose urine sample for PK
- Randomly assign the subject to either AT-007 or placebo (Note: Unblinded CRU pharmacist will have the randomization schedule.)

Then, study drug (AT-007 or placebo) will be administered to the subject, and the following procedures will be done on Day 1 after the dose:

- For Cohorts A4 and A5 only, collect postdose urine for PK
- Collect postdose blood samples for PK
- Conduct postdose 12-lead ECG
- Measure postdose vital signs
- Feed the subject (3 meals with breakfast provided at ≥ 2 hours postdose)

Note: Blood/urine collection for PK will continue into Day 2.

AE and concomitant medication data will be collected both before and after dose administration on Day 1.

6.4.2. Days 2 and 3

Subjects will remain in the CRU on Day 2. Subjects in Cohorts A4 and A5 only will also remain in the CRU on Day 3.

The following procedures will be done:

- Measure vital signs on both days
- Collect AE and concomitant medication data on both days
- Collect postdose blood sample(s) for PK on both days
- For Cohorts A4 and A5 only, collect postdose urine for PK on both days (Note: Urine collection for PK will continue into Day 4.)
- Feed the subject (3 meals on Day 2)
- Additional Day 3 Procedures
 - Perform physical examination including weight
 - Conduct 12-lead ECG
 - Collect fasting blood sample(s) for clinical laboratory testing (hematology, coagulation and biochemistry)
 - Collect fasting urine sample for urinalysis and, for female subjects of childbearing potential only, urine pregnancy test
 - Schedule the EOS Visit for Day 28 (± 2 days)
 - Discharge subject from the CRU (Cohorts A1, A2, and A3 only) and remind subject/caregiver to fast overnight for at least 10 hours on the day before the EOS Visit and return to the CRU for the EOS Visit before breaking the fast
 - Feed the subject (3 meals) (Cohorts A4 and A5 only)

6.4.3. Day 4

Day 4 procedures apply only to Cohorts A4 and A5.

The following procedures will be done on Day 4:

- Finish the urine collection for PK
- Collect AE and concomitant medications data
- Schedule the EOS Visit for Day 28 (± 2 days)

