b: The EOS visit will be scheduled for 28 (±2) days after the dose of study drug.

c: All physical examinations will include weight; however, height will be measured only at screening.

d: Vital signs will be measured at Screening, Day -1 check-in, predose (within 60 min before the dose) on Day 1, at 4 hours (±10 minutes) after the dose on Day 1, once daily on Days 2 and 3, and at the EOS visit.

e: Electrocardiograms will be performed at Screening, Day -1 check-in, predose (within 60 min before the dose) on Day 1, at 2 hours (±10 minutes) after the dose on Day 1, on Day 3, and at the EOS visit.

f: Samples for clinical safety laboratory tests will be collected under fasting conditions.

- g: Serum pregnancy tests at Screening, Day -1, and EOS visits; urine pregnancy tests at other time points. Also, female subjects claiming postmenopausal status will have that status verified with an FSH test at Screening. Once a female subject is verified as postmenopausal or otherwise not of childbearing potential, the subject is exempt for further pregnancy tests.
- h: Blood samples for PK will be collected predose (within 60 min before the dose) and at 0.5, 1, 1.5, 2, 4, 6, 8, 12, 24, 36, and 48 hours (\pm 5 minutes for all time points) after the dose.
- i: Urine for PK will be collected predose (spot collection within 60 min before the dose) and in 4-hour intervals (0 to 4, >4 to 8, >8 to 12, >12 to 16, >16 to 20, and >20 to 24) through the first 24 hours after the dose followed by 12-hour intervals (>24 to 36, >36 to 48, >48 to 60, and >60 to 72) from 24 hours postdose to 72 hours postdose. Allowable windows for urine collection container changes will be \pm 30 minutes through the first 24 hours and \pm 1 hour thereafter.
- j: Cohort A4 = highest originally planned dose level cohort in Part A. Cohort A5 = highest planned dose level cohort in Part A after the protocol amendment resulting in protocol version 4.0.

**APPENDIX B. SCHEDULE OF ASSESSMENTS FOR PART B (MAD IN
HEALTHY SUBJECTS)**

Schedule of Assessments for MAD in Healthy Subjects (Part B)

PROCEDURE	Screening (Days -28 to -1)	Day -1 ^a (Check-in)	Day 1	Day 2	Days 3, 4, & 5	Day 6	Day 7	Day 8	Day 9 ^a (Check-out)	EOS Visit ^b (Day 35±2)
Check-in		X ^a								
Discharge									X ^a	
Informed consent	X									
I/E criteria	X	X								
Medical history/updates	X	X								X
Demographic data	X									
Physical examination ^c	X	X				X			X	X
Vital signs ^d	X	X	X	X		X	X	X	X	X
Electrocardiogram ^e	X	X	X				X			X

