3.2.5 Physical Examinations

Physical examinations will be performed as follows:

- Part A: Screening; Days -1 and 3; and EOS
- Part B: Screening; Days -1, 6, and 9; and EOS
- Part C: Screening; Days -1, 6, and 9; and EOS
- Part D: Screening; Days -1, 6, 12, 20, 32, and 34; and EOS
- Part E: Screening; Days -1, 6, 12, 20, 32, and 34; and EOS
- Part D Extension: Screening; Days -1, 30, 60 and 90; and EOE

Height will be measured at screening. Weight will be measured as part of all physical examinations. Any time during the study after the first dose of study drug, abnormal findings considered to be clinically significant by the Investigator/designee will be reported as AEs.

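### The mandatory stop and the MTD count events only to 24 hours after the last dose; in Part A, and possibly for single-dose-only subjects in D3 and Part E, that ends before the SRC data cut

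*Protocol*

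**What the plan says.** Protocol 3.5 has two mandatory triggers for stopping escalation and starting de-escalation. The first is two or more AT-007 subjects who "experience a DLT at any time through 24 hours after the last dose of study treatment". The second is any AT-007 subject with a "fatal SAE or life-threatening SAE requiring urgent intervention at any time through 24 hours of the last dose of study treatment". The MTD is the dose level below the one at which a trigger occurs. If neither occurs in a part, "then the MTD will be the highest dose level in that study part". SAP 3.1.4.7 repeats both triggers with the same window, and the default.

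The DLT definition in 3.5 carries no time limit. It covers AT-007-related adverse events and relevant findings on laboratory tests, ECGs, vital signs or physical examination. Neither document says in the rule whether *last dose* is the last dose scheduled or the last dose the subject took.

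Protocol 3.4 allows progression to the next cohort only after review of "safety data through Day 3 in Part A, Day 8 in Parts B and C, and Day 12 in Parts D and E".

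**The concern.** The window suits a week of daily dosing. After a single dose it is short compared with what the committee sees. An event that starts 36 hours after a single dose is in the SRC's Part A data but cannot count toward the mandatory stop or lower the MTD.

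The two triggers and the MTD are the parts of the escalation plan that leave no room for judgement. A discretionary stop does not alter the MTD default, and Protocol 3.6 uses the MTD: the study ends if exposure at the MTD is insufficient. Because *last dose* is undefined, the same events in Parts D and E could also be counted or not, depending on how the term is read.

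**Working it through.** The plan states no operating characteristics for this rule, so there is no figure to reproduce. The check compares the day on which the count closes with the SRC data cut.

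**Inputs.** The window is 24 h (Protocol 3.5). SRC cuts are from 3.4. Dosing days are from 3.3.1 to 3.3.5: Day 1 in Part A; Days 1 to 7 in B and C; Day 1, then Days 6 to 32, in D and E. Planned active subjects per cohort are 6 in Part A (Table 2) and 4 in Parts D and E (Tables 5 and 6).

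**Step 1: day count.**

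| Subjects | Last dose | Count closes | SRC cut | Reviewed or washout time not counted |
|---|---|---|---|---|
| Part A | Day 1 | Day 2 (24 h) | Day 3 (48 h) | 48 − 24 = 24 h; 24/48 = 50% |
| B/C, all 7 doses | Day 7 | Day 8 | Day 8 | none |
| D/E, continuing | Day 32 | Day 33 | Day 12 | none; washout events precede the last dose and count |
| D/E, Day 1 dose only, *last dose* = received | Day 1 | Day 2 | Day 12 | washout 5 × 24 = 120 h; 120 − 24 = 96 h; 96/120 = 80% |
| D/E, Day 1 dose only, *last dose* = scheduled | Day 32 | Day 33 | Day 12 | 0 of 120 h |

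**Step 2: what falls inside the Part A count.** Adverse events are collected on Days 1 and 2, an ECG is taken at 2 h and vital signs at 4 h (Protocol 6.4; Appendix A, footnotes d and e). Laboratory tests, physical examination and a further ECG come under "Additional Day 3 Procedures" in 6.4.2. The SAP agrees on laboratory times, "Part A: Screening, Day -1, Day 3, EOS", and on examinations, "Part A: Screening; Days -1 and 3; and EOS". So no scheduled post-dose laboratory test or physical examination falls within 24 h. An event that began within 24 h and was detected on Day 3 still counts. For a laboratory abnormality first measured on Day 3, however, no earlier scheduled post-dose sample can date its onset.

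**Step 3: the undefined term in D/E.** The Synopsis, on Part D non-completers entering the Extension, uses the dose actually received. The note to Table 9 puts the day of last dose at Day 32, but as a PK term. The documents do not settle which meaning 3.5 intends.

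**Step 4: a worked case.** Take E1 with E2 planned, and 2 of 4 active subjects who have a DLT in the washout and do not advance. The threshold is 2.
- Onset at 20 h: 20 ≤ 24, so 2 are counted and the stop is mandatory under either reading.
- Onset at 36 h, dose received: 36 > 24, so 0 are counted and there is no mandatory stop.
- Onset at 36 h, scheduled Day 32: 2 are counted and the stop is mandatory.

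**Step 5: how many subjects this can touch.** For a mandatory stop on planned escalation, only Part E cohorts followed by another cohort matter: 0, 1 or 2 cohorts × 4 active = 0, 4 or 8 subjects. Through de-escalation and the MTD alone, D3 and the last Part E cohort matter: 4 + 4 = 8. In Part A, 5 × 6 = 30 AT-007 subjects were planned and no DLT was identified in any cohort (Protocol 1.4), so the retrospective effect is nil.

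**Step 6: illustration with assumed rates.** Let *p* be the true DLT rate and *f* the share of DLTs starting inside the window; neither is in the documents. With q = p·f, P(at least 2 counted) = 1 − (1 − q)^n − n·q·(1 − q)^(n−1).

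| n active | p | f = 1 | f = 0.75 | f = 0.5 | f = 0.25 |
|---|---|---|---|---|---|
| 6 | 0.20 | 0.345 | 0.224 | 0.114 | 0.033 |
| 6 | 0.33 | 0.642 | 0.460 | 0.259 | 0.082 |
| 6 | 0.50 | 0.891 | 0.726 | 0.466 | 0.167 |
| 4 | 0.20 | 0.181 | 0.110 | 0.052 | 0.014 |
| 4 | 0.33 | 0.401 | 0.258 | 0.130 | 0.036 |
| 4 | 0.50 | 0.688 | 0.481 | 0.262 | 0.079 |

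The rows for n = 4 apply to D/E only under the dose-received reading and if subjects with late DLTs are not advanced.

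**The case against.** The best defence is that late events are already handled. Progression depends on all safety data to the SRC cut, with no 24-hour limit (Protocol 3.3.1, 3.3.4, 3.3.5). Section 3.4 lists DLTs among the data assessed, and the SRC or Sponsor may stop at any time. The Sponsor is unblinded in D and E and must agree before any subject starts multiple dosing. All of this stands. A reader might infer that escalation could proceed over late events nobody had looked at; the documents do not support that.

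The live branches are also remote. Part A is finished and no further cohort is planned there. E2 and E3 are optional, and D3 is the highest planned Part D cohort. Doses above 40 mg/kg require no DLT up to that dose, with no time window, and no AT-007 detected in the Cohort C3 CSF; Protocol 1.2 describes the drug as CNS penetrant, so that condition looks hard to meet. The Part E starting dose and DE2 rest on acceptability and tolerability, not on the MTD. The MTD is not an objective or endpoint and has no table in the SAP. These points limit the size of the concern but do not remove it, because discretion does not change the MTD default.

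A reader might also infer that any single-dose event after 24 hours in D and E goes uncounted. That is wrong for subjects who continue, whose washout events precede their last dose.

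Finally, the fix still has a cut-off, and nothing in the documents shows 24 hours to be pharmacologically too short. That is fair. The case for change is only that the rule should count what the SRC already reviews.

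**Conclusion.** The point holds in a narrow form and is minor. As written, the Part A count closes a day before the SRC cut and before the first scheduled post-dose laboratory tests and physical examination. This has no retrospective effect on DLT counts, and no missed event is shown.

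What remains live is:
- the mandatory stop before E2 and E3, if those cohorts open;
- de-escalation and the MTD in D3 and the last Part E cohort;
- any single-dose cohort above 40 mg/kg, should one open.

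The first two require both that *last dose* means the dose received and that the affected subjects do not advance past Day 1. If the scheduled Day 32 dose is meant, D and E have no gap. Only the non-discretionary stop and the MTD are affected. The subject counts assume the planned 4 active subjects per D/E cohort.

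**What to change.** In Protocol 3.5 and SAP 3.1.4.7, define *last dose* as the last dose the subject received. Count DLTs and fatal or life-threatening SAEs with onset through the later of (a) 24 hours after that dose and (b) the part's SRC data cut: Day 3 in Part A, Day 8 in B and C, Day 12 in D and E. Leave the DLT definition and SRC timing as they are.

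Subjects who take all 7 doses in B and C stay at Day 8, and D/E subjects who complete multiple dosing stay at Day 33. In the worked case, 2 events are counted whether onset is at 20 or 36 hours.

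The text is a sentence or two in each document. It uses data already collected and reviewed, with no new procedure and no delay to SRC meetings. The costs are a rule that may trigger slightly more often and a routine protocol amendment with IRB/IEC review.
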